4.2.2 Surgery

Surgical control of primary and metastatic sites of disease may include control of either or both sites of disease as determined by the multidisciplinary group (medical oncologist, radiation oncologist, and surgeon).

4.2.2.1 Primary Site

Surgical resection can be performed by open thoracotomy, video assisted thoracoscopy or robotic assisted thoracoscopy as determined by the surgeon as long as all residual disease can be resected.

Surgery of the primary site may consist of a lobectomy, sleeve resection, wedge resection or pneumonectomy as determined by the attending surgeon based on the operative findings. The type of resection should provide complete removal of the primary lesion with negative gross margins and microscopic margins (if possible). Limited resection is allowed if negative gross margins can be achieved. Documentation of microscopic margins (bronchial and vascular) by frozen section at surgery is not mandatory but encouraged.

Lesions found to have direct extension into parietal pleura or chest wall should be resected if possible with an en-bloc chest wall resection. Similarly, lesions with direct extension to pericardium or diaphragm

should have an en-bloc resection of these structures if possible with an attempt to achieve negative gross margins.

A complete mediastinal lymph node sampling is encouraged. For right-sided lesions, this includes 2R, 4R, 7, 8 and 9. For left-sided lesions, this includes 4L, 5, 6, 7, 8 and 9.

4.2.2.2 Metastatic Sites

Surgical resection of metastatic sites can be performed by open thoracotomy, video assisted thoracoscopy/laparoscopy or robotic assisted thoracoscopy/laparoscopy as determined by the surgeon as long as all residual metastatic disease can be resected with grossly negative margins. In the case of brain metastases, a postoperative MRI should be performed to confirm that a gross total resection has been achieved. Metastatic sites of disease can be controlled by a combination of radiation therapy and surgery if clinically indicated and agreed to by the multidisciplinary team (i.e., surgery and follow-up radiotherapy for CNS lesion).

4.2.3 Radiation Therapy

Radiation therapy will be delivered using external beam radiation, with either 2D/conventional techniques, three-dimensional conformal therapy, intensity modulated radiation therapy (IMRT), stereotactic radiosurgery (SRS) or proton beam therapy (PBT), at the discretion of the treating radiation oncologist.

4.2.3.1 Radiation Simulation

Patients will be simulated on a CT scanner (for fractionated radiotherapy or SRS when MRI contraindicated) or using volumetric MRI (for SRS) and immobilized based on the site of disease. Immobilization devices will be at the discretion of the treating radiation oncologist. Typical immobilization devices include a head and neck mask for metastatic sites in this region, an upper body cradle for disease in the thorax, and a lower body cradle for disease in the abdomen, pelvis, or lower extremities. A stereotactic head frame or Aquaplast mask will be used for SRS. Four-dimensional CT scanning will be utilized at the treating radiation oncologist's discretion, to assess for internal motion.

4.2.3.2 Definition of Target Volumes

Target volumes will be approved by the treating radiation oncologist, using the information obtained through clinical examination, radiologic images, the simulation planning study, and histologic specimens. When feasible and necessary, the patient's diagnostic images (CT scan, MRI study, or PET/CT imaging) will be fused with the simulation scan to delineate the suggested target volumes below.

Gross Tumor Volume (GTV) – All known disease detected by the above methods, including nodal disease.

Internal Gross Tumor Volume (iGTV) – GTV plus internal motion, if 4D scanning is obtained at the time of simulation.

Clinical Target Volume (iCTV) – iGTV plus the region at risk for microscopic spread. This target volume will be added at the physician's discretion, given that all patients in this study will have metastatic disease and thus the utility of accounting for microscopic spread is limited.

Planning Target Volume (PTV) – iGTV or iCTV plus a margin to account for patient movement and daily setup error.

Organ at Risk Volumes (OAR) – Delineation of the pertinent organs at risk, to include the lung, heart, esophagus, spinal cord, kidney, and liver.

Table 1. Summary of Suggested OAR Dose Constraints for Standard Fractionation Regimens (<3 Gy per fraction)

Target	Dose Constraint with Standard Fractionation
Brainstem	Maximum Dose <54 Gy
Optic Nerve/Optic Chiasm	Maximum Dose <54 Gy
Retina	Maximum Dose <45 Gy
Total Lung	V20<40% Mean Lung Dose<20 Gy
Liver	40%<50 Gy
Kidneys (both)	1/3<20 Gy
Esophagus	Dmax<70 Gy 50%<50 Gy
Heart	50%<30 Gy 40%<40 Gy
Spinal Cord	Maximum dose 45 Gy
Brachial Plexus	Maximum dose <60 Gy

The dose constraints for hypofractionated regimens will be adjusted based on the number of fractions. Suggested dose constraints for four, ten, and fifteen-fraction regimens are listed below.

Table 2. Summary of Suggested OAR Dose Constraints for four-fraction regimens

Organ	Volume	Dose ((Gy (RBE))
Esophagus	<= 1 cc	35 (Gy (RBE) (8.8 (Gy (RBE)/fx)
	<= 5 cc	30 (Gy (RBE) (7.5 (Gy (RBE)/fx)
Brachial Plexus	Any point	<40 (Gy (RBE)
	<= 1 cc	35 (Gy (RBE) (8.8 (Gy (RBE)/fx)
	<= 5cc	30 (Gy (RBE) (7.5 (Gy (RBE)/fx)
Trachea	<= 1 cc	40 (Gy (RBE) (8.8 (Gy (RBE)/fx)
	<= 10 cc	

Main bronchus and bronchial tree	<= 1 cc	30 (Gy (RBE) (7.5 (Gy (RBE)/fx)
	<= 10 cc	40 (Gy (RBE) (10 (Gy (RBE)/fx)
Heart	<= 1 cc	35 (Gy (RBE) (8.8 (Gy (RBE)/fx)
	<= 10 cc	40 (Gy (RBE) (10 (Gy (RBE)/fx)
Whole Lung (Right & Left, subtracting GTV)	V20 (GY (RBE)	35 (Gy (RBE) (8.8 (Gy (RBE)/fx)
	V10 (GY (RBE)	<20% (of volume)
Major vessels	V5 (GY (RBE)	<30%
	<= 1 cc	<50%
	<= 10 cc	40 (Gy (RBE) (10 (Gy (RBE)/fx)
		35 (Gy (RBE) (8.8 (Gy (RBE)/fx)
Skin	<= 1 cc	40 (Gy(RBE) (10
Chest wall	<= 10 cc	(Gy(RBE)/fx)
Spinal cord	<=50 cc	35 (Gy(RBE) (8.8
	<= 1 cc	(Gy(RBE)/fx)
	<= 10 cc	35 (Gy(RBE) (7.5
		(Gy(RBE)/fx)
		20 (Gy(RBE) (5
		(Gy(RBE)/Fx)
		15 (Gy(RBE) (3.8
		(Gy(RBE)/Fx)

Table 3. Summary of Suggested OAR Dose Constraints for ten-fraction regimens

Esophagus	<= 1 cc	50 Gy (5 Gy/fx)
	<= 10 cc	40 Gy (4 Gy/fx)
Brachial Plexus	Any point	<60 Gy
	<= 1 cc	50 Gy (5 Gy/fx)
	<= 10 cc	40 Gy (4 Gy/fx)
Trachea	<= 1 cc	60 Gy (6 Gy/fx)
	<= 10 cc	60 Gy (6 Gy/fx)
Main bronchus and bronchial tree	<= 5 cc	70 Gy (7 Gy/fx)
	<= 10 cc	60 Gy (6 Gy/fx)
Heart	<= 5 cc	70 Gy (7 Gy/fx)
	<= 10 cc	50 Gy (5 Gy/fx)
Whole Lung (Right & Left, subtracting GTV)	V20 GY	<20% (of volume)
	V10 GY	<30%
	V5 GY	<50%
Major vessels	<= 5 cc	70 Gy (7 Gy/fx)
	<= 10 cc	60 Gy (6 Gy/fx)
Skin	<= 1 cc	60 Gy(6 Gy/fx)
Chest wall	<= 10 cc	50 Gy(5 Gy/fx)
Spinal cord*	<=50 cc	50 Gy(5 Gy/fx)
	<= 1 cc	40 Gy(4 Gy/Fx)
	<= 10 cc	30 Gy(2.5 Gy/Fx)

* Spinal cord must be at least 5 mm away from 50 Gy isodose line and maximal dose is less than 42 Gy.

Table 4. Summary of Suggested OAR Dose Constraints for 15-fraction regimens, devised by calculating the biologically equivalent dose (BED) with standard fractionation and then determining equivalent doses for a 15-fraction regimen.

Target	Current Constraint at 2 Gy per fraction to 60-74 Gy	Dose Volume Constraints (BED dose assuming $\alpha/\beta=3$ with two fractionation regimens of 2 Gy x 37 fractions and 15 fractions)
Total Lung	V20<40% Mean Lung Dose<20 Gy	V17<40% Mean Lung Dose<17.5 CGE (17.1 Gy)
Liver	40%<50 Gy	40% <40 CGE (38.9 Gy)
Kidneys (both)	1/3<20 Gy	1/3 <18 CGE (17.1 Gy)
Esophagus	20%<70 Gy 50%<50 Gy	20%<55 CGE (52.65 Gy) 50% <40 CGE (38.9 Gy)
Heart	50%<30 Gy 40%<40 Gy	50% <25 Gy (24.6 Gy) 40%<32 Gy (31.9 Gy)
Spinal Cord	Maximum dose 45 Gy	Maximum dose 36 CGE (35.4 Gy)
Brachial Plexus	Maximum dose <60 Gy	<1 cc must receive 50 CGE (45.6 Gy)

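### Three entries in the suggested four- and ten-fraction organ dose tables give a total and a per-fraction dose that disagree by about 5 Gy, with no rule on which governs

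*Combined protocol and SAP*

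**What the plan says.** Section 4.2.3.2 of the combined protocol and SAP introduces the hypofractionated limits with the sentence "Suggested dose constraints for four, ten, and fifteen-fraction regimens are listed below". Two of the tables that follow fix the number of fractions in their captions: "Table 2. Summary of Suggested OAR Dose Constraints for four-fraction regimens" and "Table 3. Summary of Suggested OAR Dose Constraints for ten-fraction regimens". Apart from the lung volume limits and the brachial plexus point maximum, each limit in these two tables is a total dose followed by a bracketed dose per fraction.

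Most Table 2 entries follow a consistent pattern: "40 (Gy (RBE) (10 (Gy (RBE)/fx", "35 (Gy (RBE) (8.8 (Gy (RBE)/fx" and "30 (Gy (RBE) (7.5 (Gy (RBE)/fx". The trachea entry instead reads "40 (Gy (RBE) (8.8 (Gy (RBE)/fx". Lower in Table 2, in the block covering skin, chest wall and spinal cord, one entry pairs a total of 35 with 7.5 per fraction. In Table 3 the last entry, in the spinal cord block, pairs 30 Gy with 2.5 Gy per fraction. A footnote to Table 3 adds: "Spinal cord must be at least 5 mm away from 50 Gy isodose line and maximal dose is less than 42 Gy".

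Section 4.2.3.3 asks for the organs in Tables 2 to 4 to be contoured where their limits might be exceeded. Sections 4.2.3.4 and 4.2.3.5 leave the prescribed dose to the treating physician, guided by normal tissue tolerance and institutional standards.

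**The concern.** When the fraction count is fixed, a total and a per-fraction dose are one limit written in two ways. If they disagree, the entry states two limits. A planner working from the total and another working from the per-fraction figure would then accept different plans for the same organ, and each could point to the table.

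The trachea and the spinal cord are among the organs involved, and both matter when thoracic or spinal lesions are ablated. Safety and tolerability of LCT is a secondary objective (section 1.2), and section 3.2 refers to participating institutions, so the entries may be read by more than one team. Under section 1.3, LCT may be given in either arm. The ambiguity therefore concerns everyone who receives radiotherapy as LCT under these regimens, and not only those randomised to immediate LCT.

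**Working it through.** **Inputs.** Fractions: k = 4 (Table 2 caption) and k = 10 (Table 3 caption). The totals T and per-fraction doses f are as printed in the two tables.

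**Check.** T/k should equal f after rounding to one decimal. In reverse, f x k should return T.

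**Pairs that agree.**
- Table 2: 35/4 = 8.75 (printed 8.8); 30/4 = 7.5; 40/4 = 10; 20/4 = 5; 15/4 = 3.75 (printed 3.8). These cover 15 of 17 pairs.
- Table 3: 70/10 = 7; 60/10 = 6; 50/10 = 5; 40/10 = 4. These cover 16 of 17 pairs.

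In all, 31 of 34 pairs agree.

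**Pairs that do not agree.**

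| Entry | T | f printed | T/k | f x k | Gap (Gy) | Gap as % of T | Fractions needed (T/f) |
|---|---|---|---|---|---|---|---|
| Table 2, trachea | 40 | 8.8 | 10.0 | 35.2 | 4.8 | 12.0 | 4.55 |
| Table 2, skin/chest wall/cord block | 35 | 7.5 | 8.75 | 30 | 5 | 14.3 | 4.67 |
| Table 3, last entry, cord block | 30 | 2.5 | 3.0 | 25 | 5 | 16.7 | 12 |

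For the trachea, 35 is the total printed with 8.8 elsewhere in Table 2. Using 35 instead of 35.2, the gap is 5 Gy, or 5/40 = 12.5%. With the lower figure as the base, the gaps are 13.6% (4.8/35.2) to 14.3% (5/35), 16.7% (5/30) and 20.0% (5/25).

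**Could rounding or a different fraction count explain it?** No. The printed pairs would need 4.55, 4.67 and 12 fractions, and none of these is the count in the caption.

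**Could broken table extraction explain it?** Not the mismatches. From the trachea to the major vessels, the Table 2 dose column has slipped against its labels, but that stretch has 11 volume rows and 11 dose entries, so nothing was lost or merged. The last block has 5 rows and 5 entries. Each conflict lies inside one entry, and the Table 3 entry is on one intact line.

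**What extraction does affect.** The organ label of the 35 with 7.5 entry is uncertain. In order it is the third entry of its block, which matches the 50 cc volume and is probably chest wall. In the extracted text it sits on a spinal cord line.

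**Does other text settle it?** The Table 3 footnote caps the cord maximum below 42 Gy. It does not say whether the 10 cc limit is 30 or 25 Gy. No precedence rule was found elsewhere.

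**The case against.** The strongest reply is that these tables are advisory. The text and captions call the limits suggested, and the dose is left to the physician, normal tissue tolerance and institutional standards. A reader might infer that patients will be exposed to doses above a binding protocol limit. The documents do not support that, because no binding limit is set here and no harm is shown. The advisory status lowers the practical weight of the point, but it does not make the entries consistent. Section 4.2.3.3 also ties contouring to these limits.

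A second reply is that planners would simply use the total. The Table 2 column is headed as a dose, the per-fraction figure is in brackets, and the brachial plexus point maximum, the cord footnote and Table 4 give no per-fraction figure. This is a fair cue, so it would be too strong to say that a site has no way to choose. It remains a cue and not a stated rule.

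Third, for the spinal cord, the footnote's cap below 42 Gy limits how far the ambiguity could reach, although it does not resolve it.

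Finally, a reader might also call it an error that Table 3 prints 60 Gy (6 Gy per fraction) for the trachea at both 1 cc and 10 cc. The documents do not support that either. Both entries multiply out, and a redundant limit is not a contradiction. Nor can the trachea safely be called unique, because the skin, chest wall and cord block of Table 3 also prints 50 Gy (5 Gy per fraction) at two volumes under unclear labels.

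**Conclusion.** The point holds for three entries: two in Table 2 and one in Table 3. In each, the total and the per-fraction dose are incompatible with the stated fraction count, by 4.8 to 5 Gy. The gap is 12 to 12.5%, 14.3% and 16.7% of the printed total.

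This rests on the fraction counts in the captions and on the entries as extracted. The mismatches are secure. The organ attached to the 35 with 7.5 entry is not, and the conclusion does not depend on it.

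The consequence is an ambiguity in advisory planning limits that could lead to different plans for patients receiving LCT in either arm. It does not touch the primary endpoint, the sample size or the analysis. It is still worth correcting, because organ dose limits belong to the treatment plan and the correction is nearly free. Which half of each entry was intended cannot be determined from the documents.

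**What to change.** Check the three entries against the source constraint set and reconcile the total with the per-fraction dose in each. Reprint them so that the two figures multiply out, by 4 in Table 2 and by 10 in Table 3, and confirm the organ and volume label of the 35 with 7.5 entry at the same time. Send treating sites a short clarification. The sponsor must decide which figure stands; no value is proposed here.

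The cost is three corrected table entries and one memo. No patients, procedures or analyses change.

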3.1.1.8 Less than or equal to three metastatic lesions and no evidence of disease progression based on RECIST criteria. Note that patients that had >3 metastatic lesions in Step 1 may be eligible for enrollment in Step 2 if the number of metastatic sites is reduced to three or less.

3.1.1.9 The patient's ECOG performance status is ≤ 2 at study entry.

3.1.1.10 The patient must be a suitable candidate for LCT (radiotherapy and/or surgery) to every site of disease, as determined by the treating physician(s). Consultation with a multidisciplinary team, including a medical oncologist, radiation oncologist, and thoracic surgeon, is encouraged but not required.

3.1.1.10.1 Concurrent chemoradiation is permitted as consolidative therapy. The following concurrent therapies are permitted: Tyrosine kinase inhibitors (i.e., erlotinib) – can be delivered with both hypofractionated (≥ 3 Gy per fraction) and standard fractionated radiation therapy (<3 Gy per fraction); platinum-based chemotherapy – standard fractionated radiation therapy (<3 Gy per fraction)

3.1.1.10.2 Bevacizumab will not be permitted within 2 weeks of the initiation of the radiation therapy course

3.1.1.10.3 Treatment to central nervous system lesions, such as the brain or spine (prior to first line systemic therapy), or symptomatic lesions requiring urgent palliative radiation, is permitted prior to randomization, in which case the patient would be randomized to treatment of other metastatic sites or the primary sites (based on the disease remaining after first-line treatment). These treated lesions should be counted towards the total number of metastases at the time of enrollment.

3.1.1.11 The patient is $>/= 18$ years of age.

3.1.1.12 The patient has signed informed consent.

3.1.1.13 Women of childbearing potential must agree to use adequate contraception (hormonal or barrier method of birth control; abstinence) for the duration of study participation and for six (6) months after discontinuation of the study drugs. Childbearing potential will be defined as women who have had menses within the past 12 months, who have not had tubal ligation, hysterectomy or bilateral oophorectomy. Should a woman become pregnant or suspect that she is pregnant while participating in this study, she should inform her treating physician immediately. The patient, if

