4.2.3.5 Metastatic Sites

Radiation to the metastatic sites can be delivered with 2D/conventional techniques, 3D conformal therapy, IMRT, SRS, or PBT, at the discretion of the treating radiation oncologist. Radiation simulation is dependent on the site being treated, and immobilization devices include but are not limited to upper body cradles, stereotactic body cradles, lower body cradles, SRS immobilization, or a head and neck mass.

The radiation dose to metastatic sites will be determined by the treating physician and based on normal tissue tolerance and institutional standards.

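### Table 3's ten-fraction spinal cord maximum (<42 Gy) is looser than Table 4's 15-fraction cap (36 CGE / 35.4 Gy) at any alpha/beta, although Section 4.2.3.2 says hypofractionated limits are adjusted for fraction number.

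*Combined protocol and SAP*

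**What the plan says.** Before the hypofractionated tables, Section 4.2.3.2 states: "The dose constraints for hypofractionated regimens will be adjusted based on the number of fractions". The next sentence brings all three tables under that statement: "Suggested dose constraints for four, ten, and fifteen-fraction regimens are listed below".

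The cord limits compared here are:

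- Table 1 (standard fractionation, below 3 Gy per fraction): "Maximum dose 45 Gy".
- Table 3 (ten fractions), footnote: "Spinal cord must be at least 5 mm away from 50 Gy isodose line and maximal dose is less than 42 Gy".
- Table 4 (15 fractions), cord row: "Maximum dose 36 CGE (35.4 Gy", the second figure being given in parentheses. The table heading says its limits were "devised by calculating the biologically equivalent dose (BED) with standard fractionation and then determining equivalent doses for a 15-fraction regimen", and its column heading gives alpha/beta 3 and a reference course of 37 fractions.

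Section 3.1.1.10.1 puts the boundary for hypofractionation at 3 Gy per fraction; concurrent tyrosine kinase inhibitors "can be delivered with both hypofractionated (≥ 3 Gy per fraction) and standard fractionated radiation therapy (<3 Gy per fraction". On dose, Section 4.2.3.5 says: "The radiation dose to metastatic sites will be determined by the treating physician and based on normal tissue tolerance and institutional standards". All four tables are headed as suggestions, although the Table 3 footnote is worded as a requirement. The documents give no derivation for Table 3.

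**The concern.** With fewer and larger fractions, a limit on a late-responding organ would be expected to fall in total dose. Here the cord maximum rises from 36 to just under 42 as the course shortens from 15 fractions to ten. The 5 mm rule in the footnote is an extra geometric condition and does not lower the 42 Gy figure.

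The treating physician chooses dose and fractionation, and Section 4.2.3.3 tells sites to contour organs when a limit in Tables 2 to 4 may be exceeded. The figures therefore guide planning. A lesion near the cord gets a more permissive cord limit if it is treated in ten fractions than in fifteen, and the plan does not say why.

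**Working it through.** **Inputs.** Table 3 footnote: <42 Gy in 10 fractions, so up to 4.2 Gy each. Table 4: 36 CGE (35.4 Gy) in 15 fractions; 36/15 = 2.4. Table 1: 45 Gy. Alpha/beta of 3 is stated for Table 4 only, so applying it to Table 3 is an assumption and is varied below. CGE is treated as Gy; using 35.4 Gy instead would widen the gap.

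**Formulas.** BED = D(1 + (D/n)/ab), where D is total dose, n the number of fractions and ab is alpha/beta. Inverted: D = (n·ab/2)(−1 + √(1 + 4·BED/(n·ab))).

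**Step 1: reproduce Table 4's cord figure.** Spread 45 Gy over 37 fractions (1.216 Gy each) at ab = 3: BED = 45(1 + 1.216/3) = 63.2. The equivalent in 15 fractions is 22.5(−1 + √(1 + 4×63.2/45)) = 35.4 Gy, which matches. The same method returns the printed lung and kidney (17.1), liver (38.9) and heart (24.6, 31.9) figures, and oesophagus to within rounding (52.62 against 52.65). It comes close on brachial plexus (45.8 against 45.6).

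Converting 45 Gy at 2 Gy per fraction (BED 75.0) would instead give 39.8 Gy in 15 fractions. Table 4's cap is therefore strict, because it assumes about 1.2 Gy per fraction for the reference course.

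**Step 2: ordering without any alpha/beta.** 42(1 + 4.2/ab) exceeds 36(1 + 2.4/ab) for every positive ab, because 42 > 36 and 4.2 > 2.4. The same holds against a 15-fraction cap of 39.8 Gy (2.65 Gy per fraction).

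**Step 3: size against Table 4.**

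| ab | BED, 42 in 10 | BED, 36 in 15 | Excess |
|---|---|---|---|
| 2 | 130.2 | 79.2 | 64% |
| 3 | 100.8 | 64.8 | 56% |
| 4 | 86.1 | 57.6 | 49% |
| 10 | 59.6 | 44.6 | 34% |
| limit, ab → ∞ | 42 | 36 | 17% |

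**Step 4: size against Table 1.** At ab = 3, 45 Gy has BED 75.0 at 2 Gy per fraction and 90.0 at the 3 Gy bound. The excess of 42 in 10 is 100.8/75.0 = 1.34 (34%) and 100.8/90.0 = 1.12 (12%). Solving 42(1 + 4.2/ab) > 45(1 + f/ab) gives ab < (176.4 − 45f)/3, which is 28.8 for f = 2 and 13.8 for f = 3. This comparison, unlike Step 2, does depend on alpha/beta.

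**Step 5: ten-fraction equivalents at ab = 3.**

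- To match 45 Gy over 37 fractions (Table 4's own method): 31.1 Gy.
- To match 36 in 15: 15(−1 + √(1 + 4×64.8/30)) = 31.6 Gy. Over ab 2 to 10 this runs from 31.0 to 33.5 Gy, and it stays below 36 Gy for any ab.
- To match 45 Gy at 2 Gy per fraction: 15(−1 + √11) = 34.7 Gy. This is BED 75.0 against 64.8, so 16% looser than the present Table 4 cap.

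**Step 6: the labelled entries in Table 3.** Seventeen entries give a dose per fraction. Sixteen divide to ten fractions (50/5, 40/4, 60/6, 70/7). The remaining one, 30 Gy at 2.5 Gy per fraction, gives 30/2.5 = 12. That slip stands whichever organ row it belongs to. Assigning it to the cord at ≤10 cc, and the 40 Gy entry to the cord at ≤1 cc, is a reading only, because the last rows of the table are shifted in the available text. If the 40 Gy entry is the cord row, its BED at ab = 3 is 40(1 + 4/3) = 93.3, also above Tables 1 (at 2 or 3 Gy per fraction) and 4.

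**The case against.** The strongest reply is that no stated rule is broken. The plan promises adjustment for fraction number. It does not promise equal BED, and only Table 4 is said to be BED-derived. Table 3 has a different format, small-volume limits plus a distance rule, and may have a clinical or institutional basis that the documents do not give. This stands in part: a reader might infer that Table 3 misapplies a BED rule, and the documents do not support that. The ordering in Step 2 needs no such rule, though, and a limit that rises as fractions grow larger sits badly with the statement that introduces the tables.

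A reader might also infer that one treatment faces two contradictory ceilings. It does not. A ten-fraction course uses Table 3 and a 15-fraction course uses Table 4, so both can be followed.

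The 56% is also open to challenge, because Table 4's reference course makes its cap strict. That is correct, and the 34% against 45 Gy at 2 Gy per fraction belongs beside it.

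Finally, the limits are suggestions, and dose also follows normal tissue tolerance and institutional standards. That lowers the stakes but does not explain the difference between the tables.

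**Conclusion.** The point holds as an inconsistency in stringency between regimens. The ten-fraction cord ceiling is looser than the 15-fraction cap at every alpha/beta. It is looser than Table 1's 45 Gy at any alpha/beta below 13.8 at the 3 Gy per fraction bound, or below 28.8 at 2 Gy. At alpha/beta 3 the excess in BED is 56% over Table 4 as printed and 34% over 45 Gy at 2 Gy per fraction. These percentages rest on the linear-quadratic model, on carrying Table 4's alpha/beta over to Table 3, and on treating CGE as Gy. The ordering against Table 4 does not depend on the alpha/beta chosen or on table row alignment.

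A reader might go further and conclude that 42 Gy in ten fractions is unsafe. The documents give no cord injury rate, so that cannot be shown from them. PFS, type I error and power are not affected.

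**What to change.** Lower the Table 3 cord maximum so that it is no looser than the 15-fraction cap. That means below 36 Gy at any alpha/beta, and about 31 to 32 Gy at alpha/beta 3: 31.1 Gy by Table 4's own method, or 31.6 Gy to match 36 in 15.

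If the sponsor prefers to anchor on 45 Gy at 2 Gy per fraction, use about 34.7 Gy in ten fractions and restate Table 4's cord cap at about 39.8 Gy, so that the two agree. Adopting 34.7 Gy alone would leave Table 3 looser than Table 4. Restating only the cord row would put it on a different basis from the rest of Table 4, which should be noted in the table. Under either option the sponsor's radiation oncologists should confirm the value.

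Check the apparent ≤1 cc cord entry (40 Gy) against the original table and bring it into line. Check the intended total for the 30 Gy entry and correct its label; 30 Gy in ten fractions is 3 Gy per fraction.

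The cost is a small amendment to the Table 3 footnote and up to two entries (plus Table 4's cord row under the second option), with a note to sites. The downside is that some ten-fraction plans near the cord may need re-planning or a different fractionation.

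### Table 4's 15-fraction brachial plexus limit (and, less so, its oesophagus 20% and kidney limits) does not follow the table's stated BED derivation, and Tables 1 and 4 start from different oesophagus rules

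*Combined protocol and SAP*

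**What the plan says.** Section 4.2.3.2 of the combined protocol and SAP gives four tables of suggested organ-at-risk limits. Table 1 covers standard fractionation (under 3 Gy per fraction) and Table 4 covers 15 fractions.

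- **Derivation.** Table 4's caption says the limits were "devised by calculating the biologically equivalent dose (BED) with standard fractionation and then determining equivalent doses for a 15-fraction regimen". The column heading fixes alpha/beta at 3 and names "two fractionation regimens of 2 Gy x 37 fractions and 15 fractions" as the schedules compared. The left-hand column is headed as the existing constraint at 2 Gy per fraction.
- **Brachial plexus.** The standard constraint is "Maximum dose <60 Gy" in both tables. Table 4's 15-fraction entry is "<1 cc must receive 50 CGE (45.6 Gy)".
- **Oesophagus.** Table 1 gives "Dmax<70 Gy 50%<50 Gy". Table 4's left-hand column gives "20%<70 Gy 50%<50 Gy".
- **Status.** All four tables are labelled as suggestions. Sections 4.2.3.4 and 4.2.3.5 leave dose to the treating physician, guided by tissue tolerance and institutional standards. Section 4.2.3.3 ties contouring to the risk of exceeding the limits in Tables 2 to 4.

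**The concern.** Nearly every 15-fraction entry in Table 4 carries two numbers: a limit, then a lower figure in brackets. If the caption is taken at its word, the limit should be the equal-BED dose. For the brachial plexus the two numbers are too far apart to pass as the same quantity, and the row also changes what is being limited. The abbreviation CGE is attached to most first figures and is not defined, so a planner cannot tell whether the pair is a limit with its derivation, a unit conversion, or two alternative limits.

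The oesophagus raises a second question. Table 4's starting constraint for 2 Gy fractions ought to match Table 1, whose scope includes 2 Gy fractions, and it does not. The 15-fraction limit was then built on Table 4's version.

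At stake is whether two planners reading these tables would hold these organs to the same limit.

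**Working it through.** **Inputs.** Alpha/beta = 3, 37 and 15 fractions, and the constraint doses D, all from Table 4.

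**Formulas.** An organ receiving total dose D over 37 fractions has BED = D × (1 + D/(37 × 3)) = D × (1 + D/111). The 15-fraction dose d of equal BED solves d × (1 + d/45) = BED, so d = 22.5 × (√(1 + 4 × BED/45) − 1).

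**Reproducing the brackets (brachial plexus).** BED = 60 × (1 + 60/111) = 92.4, and d = 22.5 × (√(1 + 4 × 92.43/45) − 1) = 45.81 Gy. The table prints 45.6.

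**Alternative basis.** Taking the left-hand column heading literally, with the organ itself receiving 2 Gy per fraction, BED = D × (1 + 2/3). For 60 Gy this is 100.0, and d = 48.3 Gy.

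| Row | D | Equal BED, 37-fraction basis | Bracket | Printed limit | Limit over bracket | Equal BED, strict 2 Gy |
|---|---|---|---|---|---|---|
| Lung volume limit | 20 | 17.10 | none | 17 | – | 22.3 |
| Mean lung dose | 20 | 17.10 | 17.1 | 17.5 | +2.3% | 22.3 |
| Liver | 50 | 38.90 | 38.9 | 40 | +2.8% | 42.7 |
| Kidneys | 20 | 17.10 | 17.1 | 18 | +5.3% | 22.3 |
| Oesophagus 20% | 70 | 52.62 | 52.65 | 55 | +4.5% | 53.4 |
| Oesophagus 50% | 50 | 38.90 | 38.9 | 40 | +2.8% | 42.7 |
| Heart 50% | 30 | 24.63 | 24.6 | 25 | +1.6% | 30.0 |
| Heart 40% | 40 | 31.86 | 31.9 | 32 | +0.3% | 36.7 |
| Spinal cord | 45 | 35.40 | 35.4 | 36 | +1.7% | 39.8 |
| Brachial plexus | 60 | 45.81 | 45.6 | 50 | +9.6% | 48.3 |

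The 37-fraction basis matches every bracket within 0.5%; the strict 2 Gy basis matches none. The brackets are therefore the derived values, and the first figures are something else.

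**Size of the departures.**

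- Brachial plexus: 50/45.81 = 1.09 and 50/48.3 = 1.036. The dose 50 in 15 fractions has BED 50 × (1 + 50/45) = 105.6, the same as 66.1 Gy in 37 fractions or 105.6/(5/3) = 63.3 Gy at 2 Gy per fraction.
- Oesophagus 20%: 55/52.65 = 1.045 and 55/53.4 = 1.03.
- Kidneys: 18/17.1 = 1.053, but 18 is below the 22.3 of the strict basis.

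**Could CGE be a unit conversion?** The ratio of limit to bracket runs from 1.003 to 1.096, so no single factor fits. The heart row gives both figures in Gy, and they still differ.

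**Change of metric.** Equal-BED conversion changes a dose. It does not turn a maximum into a limit on a volume of 1 cc.

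**Oesophagus, side by side.** For the other six organs in Table 4 the left-hand column repeats Table 1. Only the oesophagus differs: Table 1 keeps the maximum dose under 70 Gy, while Table 4 limits the dose to 20% of the organ. A plan that meets the first always meets the second; the reverse does not hold.

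**The case against.** There is a fair case that this is mostly rounding. The brackets are right and are printed openly beside the limits. Gaps of 0.3% to 2.8% look like convenient whole or half numbers, and the lung volume limit is rounded down. That stands for those rows. One might extend it and say that 45.6 and 52.65 were taken up to the next multiple of five. But 35.4 became 36 and 31.9 became 32, while a derived 17.1 appears as 17, 17.5 and 18. No single rule produces the column, and none is stated.

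On the strict 2 Gy basis, seven of the nine bracketed limits fall below their equivalents. This does not rescue the brachial plexus or oesophagus 20% entries, but it does remove the inference a reader might draw that Table 4 is loose throughout.

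A reader might also infer that the plexus maximum has in effect been raised from 60 to 66 Gy. The documents do not support that: one figure is a maximum and the other applies to a volume of 1 cc. Table 3 already gives 50 Gy to the same volume in ten fractions, where BED is 50 × (1 + 50/30) = 133.3 against 105.6 here. Table 3, however, also carries a point limit for the plexus, and Table 4 has none.

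Finally, the two oesophagus rules can both be met, and only Table 1 is addressed to standard-fractionation planning. It would be too strong to say that sites are given incompatible instructions for one regimen. What stands is that the two tables state different constraints for the same setting.

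**Conclusion.** The concern holds in a narrow form. The brachial plexus limit departs from the table's stated method by about 9% on the basis that reproduces the brackets, or about 3.6% on the strict 2 Gy reading, with an unexplained change of metric. The percentage is therefore not a like-for-like comparison of maxima. The oesophagus 20% limit is 3 to 4.5% above its equivalent on either basis; the kidney limit is about 5% above on the table's own basis only. The remaining gaps are consistent with rounding. Tables 1 and 4 differ on the oesophagus, with Table 4's version the less strict of the two.

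These results rest on the linear-quadratic BED formula with the table's own alpha/beta and fraction numbers, and on treating CGE as numerically comparable with Gy, since the documents do not define it.

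A reader might infer a demonstrated safety failure in the immediate-LCT arm. The documents do not support that: the limits are suggestions, dose is at the physician's discretion, and Sections 1.3 and 4.2.1 allow LCT in either arm. The consequence is ambiguous safety guidance for any patient given LCT by radiation. No endpoint, power figure or analysis is affected. This is a minor point.

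**What to change.** The sponsor should:

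1. reconcile the brachial plexus (value and metric), oesophagus and kidney entries in Table 4 with the stated derivation, or amend the caption to say how they were set;
2. state whether the first figure or the bracket governs, and define CGE;
3. reconcile the oesophagus constraint between Tables 1 and 4, and carry the result through to the 15-fraction entry.

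No view is taken here on which limit is right; that is for the sponsor's radiation oncology team. The cost is a table correction in a protocol amendment, with no statistical cost.
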